17.3.1. ALL AEs

All AEs will be summarized by PT, by SOC and PT, as well as by SOC, HLT, and PT. The summary by SOC and PT will also be presented for the following subgroups: sex, age group and BMI category.

Summary tables (by SOC and PT) will be generated for those AEs starting after the last dose of study drug and those AEs starting more than 1 day after the last dose of study drug.

AEs reported by $\geq 2.0\%$ (without rounding) of subjects in any treatment group will be summarized by SOC and PT.

Non-serious AEs reported by $> 5.0\%$ (without rounding) of subjects will be summarized by SOC and PT.

The summary by SOC and PT will be broken down further by maximum severity and by strongest relationship to study medication. These summaries are described in the sections below.

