11.9.8. Visit 8 (Week 6; Day 43 \pm 2 days) – Treatment Period

The following procedures will be conducted during this visit:

- Collect concomitant medications
- Vital sign measurements
- PANSS
- CGI-S
- CGI-I
- C-SSRS
- Collect adverse events

- Study drug accountability
- Dispense study drug

11.9.9. Visit 9 Telephone Contact (Week 7; Day 50 ± 2 days) – Treatment Period

The following procedures will be conducted during this visit:

- Collect concomitant medications
- C-SSRS
- Collect adverse events

11.9.10. Visit 10, End of Treatment (EOT) or Early Termination (ET) - (Week 8; Day 57 ± 2 days)

The following procedures will be conducted during this visit:

- Collect concomitant medications
- Collect nicotine use information
- Physical and neurological examination
- Vital sign measurements
- Weight and waist circumference (BMI derived in the electronic data system)
- Perform standard 12-lead ECG
- Fasted blood samples for clinical laboratory evaluation (hematology and serum chemistry) and β -hCG (for female subjects)
- Blood sample for POPPK
- Urine sample for urinalysis, rapid urine β -hCG (females), rapid urine drug screen, and UDS
- PANSS
- CGI-S
- CGI-I
- BNSS
- PSQI
- C-SSRS
- SAS
- BARS
- AIMS
- SF-12
- MSQ

- PSP
- HCRU (since last visit)
- Collect adverse events
- Study drug accountability
- Duplicate subject check

At this visit, subjects who have participated throughout the duration of the Treatment Period, up to and including Week 8 will have the option to enroll and continue treatment in an open-label extension study (Study SEP361-309).

For subjects entering the extension study, the Week 8 Visit in this study (SEP361-308) will serve as the OLE Baseline visit for the extension study (SEP361-309) and subjects will not need to return for further visits in this study.

Subjects who do not enter the extension study will complete the Follow-up Period.

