15.3.5.2. Adverse Events

Both AEs and pre-treatment events will be coded using MedDRA.

The following summaries will be provided by MedDRA SOC and PT:

- All AEs (including incidence rate and event count)
- AEs by severity (mild, moderate, severe; including incidence rate)
- AEs by relationship to study drug (related, not related; including incidence rate)

The following conventions will be followed in summarizing AEs:

- For incidence rate summaries, each subject will be counted only once within each SOC and within each PT.
- If a subject reports more than one AE within a PT and/or a SOC, the AE with the highest known severity will be used in the by severity summary. AEs with a missing severity will be assigned to the highest severity.
- For summaries by relationship to study drug, AEs will be grouped as “related” or “not related.” AEs assessed as “possible,” “probable,” or “definite,” will be grouped as “related.” AEs with a missing relationship to study drug will be regarded as related. If a subject reports more than one AE within the same SOC and PT, and any are related, the AE will be summarized as related.

Summaries of serious AEs (SAEs) and AEs leading to discontinuation will also be provided. In addition, summaries of all AEs, SAEs, and AEs leading to discontinuation by modal daily dose will be provided. The summary of AEs will include any AE occurring on or after the first dose of study drug up to 9 days following the last dose of study drug. All AEs starting after the last dose of the study drug up to 9 days following the last dose will be summarized separately. Data listings of AEs, SAEs, AEs leading to discontinuation, and deaths will be presented.

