5.1. SAFETY [SAF] POPULATION

The safety population will consist of all subjects who are enrolled and receive study medication (SEP-363856). All safety and tolerability assessments will be performed using the safety population.

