17. SAFETY OUTCOMES

Unless otherwise specified, the safety analysis and summary tables will include the column SEP-363856 50 to 100 mg/day

All analyses of the safety outcomes will be based on the SAF Population, by treatment group.

Document:	PPD		
Author:	PPD	Version Number:	1.0

Version Date:
06MAY2024

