17.3. ADVERSE EVENTS AND PRE-TREATMENT EVENTS

Adverse events (AEs) and pre-treatment events will be coded using MedDRA central coding dictionary, Version 22.0 or higher.

Any COVID-19 related Adverse Events and pre-treatment events will be identified using a pre-defined search:

Document:	PPD		
Author:	PPD	Version Number:	1.0

Table 2: Predefined search criteria for COVID-19 related adverse events or pre-treatment events.

Lower Level Term	Lower Level Term Code	Preferred Term	Preferred Term Code	Search Criteria for COVID-19 Related Adverse Events or Pre-treatment Events
Coronavirus test positive	1007025	Coronavirus test positive	10070255	Preferred Term Code = 10070255 or 10053983
Coronavirus infection	10051905	Corona virus infection	10053983	

AEs are defined as untoward medical occurrences that started at the same time of or after the first dose of study drug. Untoward medical occurrences that started prior to the first dose of study drug are pre-treatment events.

Whenever available, the time information should be accounted for in the derivation of AEs vs. pre-treatment events. In the case where time is not available, untoward medical occurrences that started on or after the day of the first dose of study drug will be considered AEs; those that started before the day of the first dose of study drug will be considered pre-treatment events.

See [APPENDIX 2](#) for handling of partial dates for AEs. In the case where it is unclear whether an untoward medical occurrence is an AE or a pre-treatment event, the algorithm uses a conservative approach where the untoward medical occurrence is classified by the worst case; i.e., AE.

AEs (including serious adverse events (SAEs)) are collected into the clinical database until the last study visit. For subjects who do not roll over to study 361-309, the last study visit will be Visit 11 (the follow-up visit) which per protocol should occur 7 (\pm 2) days after the last dose of study drug. For subjects continuing into study 361-309, the last 361-308 study visit will be Visit 10 (the end of treatment visit). If an AE (or a pre-treatment event) started in 361-308 and was ongoing at rollover, this adverse event (pre-treatment event) will be marked Ongoing in the 361-308 database. It will also be re-entered into the 361-309 database and its outcome will be monitored and updated in the 361-309 database.

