Overall summary of the incidence of all AEs, AEs related to COVID-19, study medication-related AEs, severe AEs, serious AEs, AEs leading to discontinuation from study, AEs leading to study medication withdrawal, AEs leading to study medication interruption, and AEs leading to death will be provided by treatment group. This overall incidence summary will also be separately presented for the following subgroups: country, sex, age group, number of prior hospitalizations for treatment of schizophrenia, duration of schizophrenia, and BMI category.

Listings will be provided for all AEs, AEs related to COVID-19, study medication-related AEs, severe AEs, serious AEs, AEs leading to discontinuation from the study, AEs leading to study medication withdrawal, AEs leading to study medication interruption, AEs leading to death, AEs of potential drug abuse and dependence and extrapyramidal AEs. A listing of the pre-treatment events will also be presented. When complete event start date and complete event end date are available, duration of AEs/pre-treatment events will be calculated as: event end date – event start date + 1. Duration will be presented in data listings.

Document: PPD

Author: PPD

Version Number:

1.0

Version Date:

06MAY2024

For all summaries, each subject will be counted only once within each category (e.g., an AE type, a severity level, a relationship category, a SOC, a high level term (HLT), and a PT). If not otherwise specified, all summaries will present the number and percentage of subjects as well as the number of events. For summaries by SOC and PT, AEs will be sorted by SOC based on the internationally agreed order (see [APPENDIX 4](#)) and then by PT in decreasing frequency in the “SEP-363856 50 to 100 mg/day” column. For summaries by SOC, HLT, and PT, AEs will be sorted by SOC based on the internationally agreed order and then by HLT and PT in decreasing frequency in the “SEP-363856 50 to 100 mg/day” column.

COVID-19 related pre-treatment events related pre-treatment events and AEs will be displayed similarly as any other pre-treatment events and AEs.

Document:

PPD

Author:

PPD

Version Number:

1.0

Version Date:

06MAY2024

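### The post-last-dose AE and SAE tables appear to divide by every treated subject, including those who roll over to SEP361-309 without stopping the drug, so their percentages are diluted if read as off-drug rates

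*SAP*

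**What the plan says.** **Tables.** SAP 17.3.1: "Summary tables (by SOC and PT) will be generated for those AEs starting after the last dose of study drug", and a further table for AEs starting more than 1 day after that dose. SAP 17.3.7 (numbering as in the body of the SAP) adds SAEs starting within 7 days after the last dose. Protocol 15.3.5.2 is the source: "All AEs starting after the last dose of the study drug up to 9 days following the last dose will be summarized separately".

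**Denominator.** None of these sections names one. SAP 17 supplies the default: "All analyses of the safety outcomes will be based on the SAF Population, by treatment group". SAP 5.1 requires no follow-up for membership: "The safety population will consist of all subjects who are enrolled and receive study medication (SEP-363856"). SAP 17.3 fixes the statistic: "If not otherwise specified, all summaries will present the number and percentage of subjects as well as the number of events".

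**Follow-up.** SAP 17.3: "AEs (including serious adverse events (SAEs)) are collected into the clinical database until the last study visit". For subjects who do not roll over, that visit is Visit 11, 7 (±2) days after the last dose. For the others: "For subjects continuing into study 361-309, the last 361-308 study visit will be Visit 10 (the end of treatment visit"). Protocol 11.9.10 agrees. Completers may continue treatment in SEP361-309, and those who do so "subjects will not need to return for further visits in this study".

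**The concern.** A table of AEs that start after the last dose will be read as showing what happens once SEP-363856 is stopped. Two groups share its denominator. Early terminators and completers who decline the extension stop the drug and are followed for about a week. Rollover subjects do not stop, and they leave this study's AE collection about a day after their last SEP361-308 dose. They add fully to the denominator and little or nothing to the numerator. The more subjects roll over, the lower the percentage, whatever the true off-drug risk. SAP 3.4 reports better retention and more completers than predicted, and every completer is eligible for the extension (Protocol 7.1), so the pool of possible rollovers is large.

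**Working it through.** The plan gives no post-last-dose percentage, so there is no figure of its own to reproduce.

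**Inputs**
- N = SAF size. SAP 3.4 gives 101 enrolled. I assume that all 101 were dosed.
- R = number entering SEP361-309. This is not given (SAP 9 will report it in the disposition table), so it is varied.
- x = subjects with a post-last-dose AE. I first assume that all are non-rollover subjects and that all non-rollover subjects were followed.

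**Formulas**
- Planned percentage = x/N
- Percentage among subjects who stopped = x/(N - R)
- Dilution factor = N/(N - R)

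| R | N - R | Factor | x = 5: planned | x = 5: among those who stopped | Off-drug risk of 10% is shown as |
|---|---|---|---|---|---|
| 0 | 101 | 1.0 | 5.0% | 5.0% | 10.0% |
| 25 | 76 | 101/76 = 1.33 | 5.0% | 6.6% | 7.5% |
| 50 | 51 | 101/51 = 1.98 | 5.0% | 9.8% | 5.0% |
| 71 | 30 | 101/30 = 3.37 | 5.0% | 16.7% | 3.0% |
| 81 | 20 | 101/20 = 5.05 | 5.0% | 25.0% | 2.0% |

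**How far the assumption of no rollover events holds**

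*More than 1 day after the last dose.* Dosing is at bedtime and Visit 10 is scheduled for Day 57. If the visit is on time, a rollover subject has almost no recorded time beyond 1 day, so the table applies almost as it stands.

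*After the last dose.* Rollover subjects can enter this numerator in two ways:
- an AE may start between the last bedtime dose and Visit 10;
- SAP Appendix 2 places an AE with a start date but no start time after that day's dose, so an AE on the last dosing day can count as post-dose.

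To gauge the first route, assume 7 days of follow-up for each non-rollover subject, half a day for each rollover subject (evening dose, morning visit) and the same event rate in both. Full follow-up of all 101 would be 101 × 7 = 707 person-days.
- R = 50: 51 × 7 + 50 × 0.5 = 382 person-days. Factor 707/382 = 1.85, against 1.98.
- R = 81: 20 × 7 + 81 × 0.5 = 180.5 person-days. Factor 707/180.5 = 3.92, against 5.05.

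The offset is partial. It also consists of events in subjects who were still taking the drug once daily, so it does not bring the figure closer to an off-drug rate. The missing-time rule could add more such events; the documents do not allow a count.

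*SAEs within 7 days.* The window is 7 days, but rollover subjects are observed for about one of them. Protocol 12.4.1 extends SAE reporting to the sponsor to 30 days after the last dose, but CRF recording stops at the last visit, so the table gains nothing from this.

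**Lost subjects.** Loss to follow-up and withdrawal by the subject are listed reasons for termination (Protocol 13.1). Any non-rollover subject without an AE contact after the last dose makes the number at risk smaller than N - R, and the factor larger.

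**The case against.** The strongest reply is that the percentage is correct as defined: the share of treated subjects with a recorded post-dose AE. No objective or endpoint concerns withdrawal or rebound. Counts of subjects and events are shown and the number of rollovers is reported, so a reader could work out another percentage. The definition is indeed valid, but it does not make the figure a post-treatment rate, which is the natural reading. Nor does the rollover count give a reader the number actually followed, or show which counted events came from rollover subjects.

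Four further points stand and limit the concern.

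- **The denominator is inferred.** It follows from the general rules of SAP 17 and 17.3. SAP 8 says that separate templates set the content of the tables, and these are not among the documents. A template could carry a follow-up n.
- **Rollover subjects are not barred from the numerator.** A reader might infer that they are. That is nearly true of the more-than-1-day table but not of the first table, as shown above. The more-than-1-day cut itself removes most of their between-dose events.
- **These tables are not the only look at stopping.** A reader might infer that too. Visit 11 vital signs and orthostatic findings are summarized (SAP 17.6), as is the C-SSRS at Week 9 (SAP 17.8.1).
- **The restricted percentage is not a clean off-drug risk either.** Its subjects are early terminators, including those who stopped for an AE, plus completers who declined the extension.

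**Conclusion.** The concern holds as a matter of denominator and labelling. Under the SAP's general rules, three tables divide by subjects who never stopped the drug: AEs after the last dose, AEs more than 1 day after it, and SAEs within 7 days after it. Read as off-drug rates, their percentages are diluted. For rollover subjects the dilution is nearly complete in the more-than-1-day table and partly offset in the after-last-dose table.

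The size cannot be fixed from the documents. With N = 101 and no rollover events, the factor runs from 1.0 (R = 0) through 1.33 (R = 25) and 1.98 (R = 50) to 5.05 (R = 81). Losses to follow-up would raise it. No single factor should be quoted as the bias until the rollover count is known. The primary and secondary endpoints do not use these tables and are not affected.

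**What to change.** In SAP 17.3.1 and 17.3.7, base both numerator and denominator of the post-last-dose percentages on SAF subjects who did not enter SEP361-309 and had at least one AE contact after the last dose. Show that n in the column header.

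List rollover subjects' events between the last SEP361-308 dose and Visit 10 separately. Reclassifying them as on-treatment would conflict with Protocol 15.3.5.2, which asks for all AEs after the last dose to be summarized apart; a separate listing keeps them reported.

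Record the change in SAP 3.7, which at present declares no departures from the protocol. Add a footnote saying that the group is selected: early terminators and completers who declined the extension.

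The cost is a few sentences and one denominator flag. Rollover status is already needed for the disposition table, and no new data are required. The price is a smaller n, a less favourable percentage, and a rate that describes a selected group.

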17.3.2. SEVERITY

Severity is classed as mild/ moderate/ severe (increasing severity). AEs with a missing severity will be classified as severe.

If a subject reported an AE more than once within the same SOC/ PT with different severity levels, the subject will be assigned to a severity level for that SOC/ PT based on the worst case severity (i.e., maximum severity). Event counts will not be included in this summary.

In a separate table, severe AEs will be summarized by SOC and PT.

17.3.3. RELATIONSHIP TO STUDY MEDICATION

Relationship to study medication, as indicated by the Investigator, is classed as "not related"/ "possible"/ "probable"/ "definite" (increasing strength of relationship). A "related" AE is defined as an AE with a relationship to study medication as "possible", "probable" or "definite". AEs with a missing relationship to study medication will be regarded as related to the study medication. For this summary, AEs will be presented in 2 categories, related and not related.

If a subject reported an AE more than once within the same SOC/ PT in different relationship categories, the subject will be assigned to a category for that SOC/ PT based on the worst case relationship (i.e., strongest relationship). Event counts will not be included in this summary.

In separate tables, study medication-related AEs will be summarized by SOC and PT and summarized by PT.

Document: PPD

Author: PPD

Version Number:

1.0

Version Date:

06MAY2024

17.3.4. AEs LEADING TO DISCONTINUATION FROM STUDY

AEs leading to discontinuation from the study are those AEs with “Caused Study Discontinuation” = “Yes” on the “Adverse Events” CRF form.

AEs leading to discontinuation from the study will be summarized by SOC and PT.

17.3.5. AEs LEADING TO STUDY MEDICATION WITHDRAWAL

AEs leading to permanent withdrawal from the study medication are those AEs with “Action Taken with Study Treatment” = “Drug Withdrawn” on the “Adverse Events” CRF form.

AEs leading to study medication withdrawal will be summarized by SOC and PT.

17.3.6. AEs LEADING TO STUDY MEDICATION INTERRUPTION, STUDY DOSE INCREASE AND REDUCED

AEs leading to study medication interruption, study dose increase, study dose reduce are those AEs with “Action Taken with Study Treatment” = “Drug Interrupted”, “Action Taken with Study Treatment” = “Dose Increased”, “Action Taken with Study Treatment” = “Dose Reduced” respectively on the “Adverse Events” CRF form.

AEs leading to study medication interruption will be summarized by SOC and PT.

17.3.7. SERIOUS ADVERSE EVENTS

SAEs are those AEs recorded as “Serious” on the “Adverse Events” CRF form.

SAEs will be summarized by SOC and PT. The summary will also be presented for the following subgroups: country, sex, age group, number of prior hospitalizations for treatment of schizophrenia, duration of schizophrenia, and BMI category.

In a separate table, SAEs starting within 7 days, after the last dose of study drug will be summarized by SOC and PT as well.

Document: PPD

Author: PPD

Version Number:

1.0

Version Date:

06MAY2024

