11.9.11. Visit 11 (7 ± 2 days after last dose) - Follow-up Period

All subjects who discontinue early or do not elect to enroll in the open-label extension study (Study SEP361-309) will have a safety Follow-up Visit 7 ± 2 days after their last dose of study drug. While every effort should be made to complete the Follow-up Visit in the clinic, administration of C-SSRS, and collection of AEs and concomitant medications may occur by telephone contact if the subject is unable to come to the clinic for the Follow-up Visit.

The following procedures will be conducted during this visit:

- Concomitant medications
- Physical and neurological examinations
- Vital sign measurements
- Urine sample for β hCG (for female subjects)
- C-SSRS
- Adverse events

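### The SAP's separate post-treatment SAE table stops at 7 days after the last dose, while the protocol's AE window and the follow-up visit run to 9 days

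*SAP*

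**What the plan says.** - **Protocol 15.3.5.2.** The AE summary runs from the first dose "up to 9 days following the last dose of study drug". On the off-drug part it adds: "All AEs starting after the last dose of the study drug up to 9 days following the last dose will be summarized separately". The synopsis gives the same rule.
- **Protocol 11.9.11.** Subjects who stop early or do not enter the extension study have a "safety Follow-up Visit 7 ± 2 days after their last dose of study drug".
- **SAP 17.3.** "AEs (including serious adverse events (SAEs)) are collected into the clinical database until the last study visit". For subjects who do not roll over to SEP361-309 that visit is Visit 11; for those who do, it is Visit 10.
- **SAP 17.3.1.** Summary tables by SOC and PT "will be generated for those AEs starting after the last dose of study drug", with a further table for AEs starting more than 1 day after the last dose. Neither has an upper day limit.
- **SAP 17.3.7** (numbered 17.3.5 in the table of contents). After the overall SAE table, which has no day limit, the SAP adds a separate table, also by SOC and PT, of "SAEs starting within 7 days, after the last dose of study drug".
- **SAP 3.7.** States that the analysis does not differ from the protocol. No section gives a reason for 7 days.

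**The concern.** Three rules apply to the same off-drug period: 9 days in the protocol, no limit in the SAP's post-dose AE tables, and 7 days in its post-dose SAE table. Seven is the nominal day of the follow-up visit without its allowance of 2 days. Elsewhere the SAP uses the whole follow-up period, for example for potentially clinically significant laboratory, ECG and vital-sign values (17.4, 17.5, 17.6), so the SAE table is the exception.

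What is at stake is the reading of one table. Someone who turns to it to see which serious events followed the end of treatment would reasonably take it to cover follow-up. If a late event is present in the post-dose AE table and absent here, the two outputs disagree and the reader has to work out why.

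**Working it through.** No sample-size or error-rate figure is involved; the check is on windows. Post-dose day k below means a start date k days after the last dose. It is not Study Day k (Study Day 8 is the Week 1 visit).

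**Inputs**
- Protocol limit for post-dose AEs: 9 days (15.3.5.2).
- Visit 11: 7 ± 2 days after the last dose (Protocol 11.9.11).
- End of SAE collection in the database: the last study visit (SAP 17.3).
- Limit of the separate SAE table: 7 days (SAP 17.3.7).
- Limit of the post-dose AE tables: none (SAP 17.3.1).
- An SAE is an AE meeting a seriousness criterion (Protocol 12.1.2), so an AE window also covers SAEs.
- Enrolled: 101 (SAP 3.4).

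**Step 1: the protocol's own limit.** Visit 11 can fall from 7 − 2 = 5 to 7 + 2 = 9 days after the last dose. The upper end equals the protocol's 9-day limit. The protocol does not say that 9 was chosen for this reason; the match is an inference.

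**Step 2: the gap.** 9 − 7 = 2 days, namely post-dose days 8 and 9. As a share of the longest in-window period this is 2/9 = 22%.

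**Step 3: who can fall in the gap.** Collection ends at the last visit, so exposure to the gap depends on when that visit takes place.

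| Last visit | Collected post-dose days outside the SAE table but inside the 9-day window |
|---|---|
| Visit 10, rolls over to SEP361-309 | 0 |
| Visit 11 on post-dose day 5, 6 or 7 | 0 |
| Visit 11 on post-dose day 8 | 1 (day 8) |
| Visit 11 on post-dose day 9 or later | 2 (days 8 and 9) |

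The documents give neither the rollover rate nor the timing of Visit 11, so 22% is a ceiling per subject and not an estimate for the trial.

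**Step 4: trace one event.** Take an SAE starting on post-dose day 8 in a subject whose Visit 11 is on post-dose day 9.

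| Output | Day limit | Event included? |
|---|---|---|
| Protocol 15.3.5.2 post-dose AE summary | 9 | Yes (8 ≤ 9) |
| SAP 17.3.1 post-dose AE tables | none | Yes |
| SAP 17.3.7 overall SAE table | none | Yes |
| SAP 17.3 overall incidence summary and SAE listing | none | Yes |
| SAP 17.3.7 separate post-dose SAE table | 7 | **No** (8 > 7) |

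**Step 5: size of one event.** One affected subject is 1/101 = 0.99%, about 1 percentage point of those enrolled.

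**Step 6: after the change.** With a limit of 9 the gap is 9 − 9 = 0 days. With no limit, every SAE in the post-dose AE table is also in the post-dose SAE table, including any recorded at a late Visit 11.

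**The case against.** The best defence is that nothing the protocol requires has been cut short. Protocol 15.3.5.2 asks for summaries of SAEs and for a separate summary of post-dose AEs; it does not ask for a separate post-dose SAE table. The SAP adds that table and states its window. The post-dose output that the protocol does require is kept in 17.3.1 in a more inclusive form. On this view two tables with different stated definitions need not agree, and 3.7 is not clearly wrong about the SAE table.

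Much of this stands. A reader might infer that serious events after stopping the drug are lost from the report; Step 4 shows that they are not. A reader might also infer that the 17.3.1 tables breach the protocol and should be capped at 9 days. That does not follow in any useful sense: collection stops at Visit 11, so the two rules differ only when that visit is late, and there the SAP keeps more. A cap would remove AEs recorded at a late visit from the summaries.

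The defence does not explain the 7. A supplementary table may have its own window, but here the window is shorter than the visit it draws on, shorter than the protocol's, different from its companion table, and given without a reason.

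**Conclusion.** The mismatch is real and undeclared, and small. Followed as written, SAP 17.3.7 leaves SAEs starting 8 or 9 days after the last dose out of the separate post-treatment SAE table. The effect is confined to that table and to subjects who do not roll over and are seen at Visit 11 on post-dose day 8 or later. Few such events are to be expected.

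The conclusion rests on two readings: that the 7 days are counted from the last dose, and that collection ends at the last study visit as SAP 17.3 says. The 30-day period in Protocol 12.4.1 governs reporting of SAEs to the sponsor and does not define a table window.

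It would be tempting to conclude that 22% of the off-drug safety experience is missing, or that the discontinuation endpoints are affected. The documents support neither. The first treats every subject as followed for 9 days off drug. The second has no basis, because both endpoints count discontinuations and do not use this table.

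**What to change.** In SAP 17.3.7, change the limit from 7 to 9 days, or remove it so that the table follows 17.3.1. A 9-day limit matches the protocol and closes the gap for every in-window Visit 11. Removing the limit also keeps the SAE table a subset of the post-dose AE table when Visit 11 is late. Either choice is sound; the stray comma in the sentence should be removed at the same time.

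Leave the 17.3.1 tables without a cap. Add one sentence to SAP 3.7 saying that they include all AEs collected after the last dose, whereas the protocol describes a 9-day window.

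The cost is one number or phrase in 17.3.7, the title or footnote of the matching output, and one sentence in 3.7. No new data are needed and no endpoint changes.
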